1.2 Investigational imaging method

ICG fluorescence imaging has been used to assess tissue perfusion *in vivo* in real-time intra-operative arterial and lymphatic perfusion imaging,^{25, 26} osseous flap perfusion imaging²⁷. Compared to the conventional medical imaging modalities, such as computed tomography (CT) or magnetic resonance imaging (MRI), ICG fluorescence imaging is nonionizing, low-cost, and portable. ICG is a dye that absorbs near-infrared light in the wavelength range between 790 to 805 nm and has an emission at the peak of 835 nm. ICG is almost 98% plasma protein bound so that once it takes up into the microcirculation, it remains within the lymphatic and circulatory vasculature. ICG has been approved for clinical use by FDA since 1959.²⁸ Since then, ICG has been used for human *in angiography* for ophthalmology and cardiology applications and is given routinely to patients in these clinical settings. In addition, as the clinical trials, ICG fluorescence imaging has been used to guide laparoscopic surgery,²⁹ robotic adrenalectomy,³⁰ assess tissue perfusion *in vivo* in real-time intra-operative arterial and lymphatic perfusion imaging,^{25, 31, 32} and tissue flap perfusion imaging.^{33, 34} ICG is ideal to measure perfusion/blood flow because it binds efficiently to blood lipoproteins and thus does not leak from circulation. In addition, the ICG half-life is short making repeated measures possible, and it is indirectly activated, so that the

dynamic fluorescence due to bone and tissue perfusion can be captured by a video rate imaging system.

The dynamic fluorescence imaging systems used in this study will be SPY Elite (Novadaq/Stryker). Both of them are the publicly available imaging systems that can be used to assess tissue perfusion *in real time* in the operating room. The systems have a multi-directional imaging arm which contains a near-infrared light source that illuminates the fluorescent agent within the tissues, an HD video camera that captures the intensity of fluorescent marker *in real-time*, and software that allows the user to capture relative and absolute perfusion values within the surgical

[figure not shown]

Figure 1: ICG fluorescence map overlay on the white light bone images as well as dynamic curves of green ROI. (a) baseline, (b) after double diaphyseal osteotomies, (c) half circumferential soft tissue stripping from the proximal bone close to the previous cut, (d) full circumferential soft tissue stripping from the proximal end, and (e) all circumferential soft tissue stripping to disrupt both periosteal and endosteal blood supply from entire tibia.

field. This product has been FDA approved for use to monitor blood flow, plastic surgery, microsurgery, reconstructive surgery, gastrointestinal imaging and coronary bypass surgery.

[figure not shown]

Figure 2: Summary of the maximum ICG fluorescence intensity in each ROI and condition.

supply), and (e) circumferential soft tissue stripping of the entire bone (extensively disrupting periosteal blood supply). This study protocol has been approved by Dartmouth College's Institutional Animal Care and Use Committee (IACUC). Before imaging each condition, 0.1 mg/kg ICG was injected intravenously and the dynamic fluorescence change was captured by a fluorescence surgical microscope (Pentero, Zeiss) for 4 minutes. Between imaging each condition 20 minutes was allowed for elimination of residual ICG. Figure

We have conducted work utilizing a porcine model to demonstrate measurable, reproducible and predictable differences in bone perfusion as measured by quantitative ICG fluorescence in five conditions: (a) baseline, (b) two diaphyseal osteotomies, separating 1cm of tibia with circumferential soft tissue stripping (disrupting both periosteal and endosteal blood supply), (c) ~2 cm circumferential soft tissue stripping (disrupting periosteal blood supply) from the proximal bone close to osteotomy, (d) circumferential soft tissue stripping of the entire proximal bone segment (disrupting periosteal blood

1 shows the ICG fluorescence map overlay on the white light bone images as well as dynamic curves at the proximal bones (green ROIs in middle bone models). As shown in Figure 1 the ICG intensity and dynamic changes are substantially different in different conditions and ROIs. Baseline conditions, without disruption of either periosteal or endosteal blood supplies demonstrated the highest ICG intensity. Similarly, the next highest intensity was noted in ROIs proximal and distal to the osteotomy, prior to any removal of periosteum (again, leaving endosteal and periosteal blood supply intact, however, bone disrupted by an osteotomy). As sequential soft tissue stripping was performed, sequentially removing periosteal blood supply, the ICG intensity decreased. The osteotomized fragment of bone, with both periosteal and endosteal blood supplies disrupted, demonstrated the lowest ICG intensity and a flat dynamic curve. This experiment demonstrated that ICG intensity decreased in relationship to progressive disruption in bony blood supply. To date, we have collected fluorescence data on five limbs (three pigs) for this preliminary study. Figure 2 shows the summary data of the maximum intensity of each ROIs at each condition. The data of the first leg has been excluded from this summary due to the ICG concentration and experimental condition have been changed/optimized after the first pig experiment. From this summary graph, it is clear that ICG fluorescence is highest in bone with endosteal and periosteal blood supply intact compared both with bone with periosteal blood supply disrupted/endosteal blood supply intact and bone with both periosteal and endosteal blood supply disrupted. These studies validate the effectiveness of quantitative ICG fluorescence as a method of measuring bone perfusion in a quantitative manner.

1.3 Clinical Data to Date
ICG is FDA approved for human use in angiography for ophthalmology and cardiology applications and is given routinely to patients in these clinical settings. In addition, as the clinical trials, ICG has been used to guide laparoscopic surgery,²⁹ robotic adrenalectomy,³⁰ assess tissue perfusion *in vivo* in real-time intra-operative arterial and lymphatic perfusion imaging,^{25, 31, 32} and tissue flap perfusion imaging^{33, 34}. The examples of these trials are summarized below.

- (1) Guide laparoscopic surgery²⁹ ((0.1–0.5 mg/ml/kg): This study has been carried out in Minimally Invasive Surgery Research Center, at University of Insubria, Varese, Italy. 108 ICG-enhanced fluorescence guided laparoscopic procedures were performed. ICG imaging provided high-resolution real-time images of blood flow in vessels and organs as well as highlighted biliary excretion. As the result, “no intra-operative or injection-related adverse effects were reported, and the biliary/vascular anatomy was always clearly identified.” The real-time imaging provided sufficient information to conduct a safe cholecystectomy and ensure adequate vascular supply for colectomy, nephrectomy, or find lymph nodes.
- (2) Guide robotic adrenalectomy³⁰: (3.8–20 mg/subject) This study investigates the use of ICG fluorescence to guide an accurate dissection during robotic adrenalectomy (RA). A total of 40 patients had been involved and the borders of adrenal tumors delineated by ICG imaging was superior, equivalent, or inferior to conventional robotic view in 46.5%, 25.6%, and 27.9% of the procedures, respectively.
- (3) Real-time intra-operative arterial and lymphatic perfusion imaging: ³² (2-6.6 mg/subject) 301 patients were involved in the trial, and 589 nodes were removed. 583 nodes (99%) were identified with ICG and the identify rate is higher than that the conventional 99mTc (452 nodes). No any significant acute side effects were found related to ICG in this study.
- (4) Tissue flap perfusion imaging^{33, 34}: (5 mg/subject) 77 single-pedicle breast reconstruction patients were involved. Perfusion was measured intraoperatively using ICG angiography following flap harvest and before transfer. Significant perfusion difference has been detected in various flaps and between zones. The results shown that the lower abdominal free flaps based on the inferior epigastric system have better perfusion when compared with pedicled transverse rectus abdominis muscle flaps.

1.4 Dose Rationale

We plan a sample size of 300 patients in this open label, single center, clinical trial of ICG fluorescence imaging for predicting recurrent infection in musculoskeletal trauma patients. For each subject, during the surgery, prior and after to the debridement, each of 0.1 mg/Kg ICG will be injected intravenously and video rate ICG fluorescence images will be acquired for each of 4 minutes. The ICG will

be supplied directly by Novodaq/Stryker, which is FDA approved. As it shown in Section 1.4, total dose of 0.2 mg/kg is within the range of previous studies. Indeed, this is 10 times less than the maximum recommended dose by FDA of 2mg/kg.

The subset patients who will undergo surgical treatment in CIS may undergo gadolinium (Gd-DTPA) contrast-enhanced MRI either intraoperatively or preoperatively. Gd-enhanced MRI is FDA-approved clinical imaging. The Gd-DTPA injection procedures will follow FDA-approved guidelines which are accepted as part of standard care in this setting.

1.5 Potential Risks and Benefits

The risks to subjects are minimal in relation to anticipated benefits and/or knowledge that might reasonably be expected from the results of this clinical trial.

1.5.1 Potential Risks

Risk of ICG injection: ICG (Indocyanine Green) will be administered intravenously twice: once before and once after the debridement. ICG is FDA approved for human use in angiography for ophthalmology and cardiology applications and is given routinely to patients in these clinical settings. The risks are considered minimal and consist of nausea, vomiting, hives, increased heart rate in subjects with particular sensitivity to the dye. ICG does contain sodium iodide and patients with a history of allergy to iodides will be excluded. Anaphylactic or urticarial reactions are rare but have been reported in patients both with and without a history of allergy to iodides. Anaphylactic deaths have been reported following IGG administration during cardiac catheterization. Reported rates of mild, moderate and severe adverse reactions to ICG are 0.15%, 0.2% and 0.05%. Every effort will be made to minimize this risk as much as possible. It is the standard of care at this institution to obtain information related to allergies, sensitivities and past medical histories upon patient arrival. Patients will also be monitored throughout their hospitalization, as is the standard of care, by everyone involved in their medical care for evidence of new or previously unknown reactions or sensitivities. Additionally, at all times ICG fluorescence imaging assessments are taking place, research staff and both surgical and anesthesia staff will monitor patients closely for any adverse reaction to ICG. Research staff and surgical and anesthesia staff will also monitor patients for at least 30 minutes after all ICG fluorescence assessment procedures have been completed. In the event of an unexpected allergic reaction, Dartmouth-Hitchcock Medical Center and all affiliated groups within this institution have procedures in place for managing patients with unknown or unexpected allergic reactions. If such a reaction were to occur, all standard of care treatments will be provided including but not limited to treatment with appropriate agents such as epinephrine, antihistamines and corticosteroids. Risk of infection from IV injection is also extremely rare but can occur. Pregnant women are excluded from the study. A pregnancy test is administered to women of child-bearing age as part of standard of care pre-operative testing.

Risk of dynamic contrast-enhanced magnetic resonance imaging (DCE-MRI): The risks associated with Gd contrast-enhanced MR are minimal. Gd-DTPA is an FDA-approved contrast agent and is widely used with few complications. The contrast injection procedures follow FDA-approved guidelines which are accepted as part of standard care in this setting. Consenting participants will have an intravenous catheter placed in an arm vein prior to their MRI examination by a trained MRI technologist conforming to the standard clinical methods used at DHMC.

Serious reactions to the gadolinium (Gd) are extremely rare and are primarily limited to nausea and vomiting. In response to the FDA notification regarding the potential association of nephrogenic sclerosing fibrosis (NSF) and intravenous gadolinium administration (primarily gadodiamide (Omniscan)), the Department of Radiology has developed a protocol which we will follow:

1. Identify the patients at higher risk of developing NSF (at the time of scheduling or before). Patients at risk include:

- Patients > 50y
- Patients already on dialysis
- Patients with known renal insufficiency but not currently on dialysis
- Diabetic patients

- Patients with known cardiovascular disease
- Patients who will be receiving high dose gadolinium (e.g. MR angiograms)
- Hypertensive patients

2. Obtain estimated Glomerular filtration rate (GFR) on this higher risk group of patients (unless already on dialysis).

- If a GFR value has been checked and is available in the patient's medical record within 1 month of contrast-enhanced MR, that value will be acceptable.
- If the participant is not a patient at DHMC, a "stat" GFR will be performed at DHMC one (1) hour prior to contrast-enhanced MR scan.

Subjects with a GFR <30 ml/min. will be considered ineligible for the contrast enhanced MRI portion of the study.

GFR values will not be sought at the time of scheduling on low risk patients, but the scheduler will check medical records at the time of the scan to see if an incidental GFR value is available.

Risk of infection from IV injection is also extremely rare but can occur. MR examination is used daily for many conditions and is considered safe. There are no known risks with MR imaging. Some individuals may feel claustrophobic inside the MR unit. Metal implants, such as surgical clips, and electronic devices, such as pacemakers, can be contra-indications for MR exams. Participants are questioned about these conditions and not enrolled accordingly.

Prolonged operating room time: Because the ICG fluorescence assessments will take place in the operating room, participation in this study may increase the amount of time spent under surgical anesthesia in the operating room. For the average case, an additional 10 minutes at most will be incurred. However, the research staff will make every effort to minimize this risk by performing the assessment test while other required operative procedures are being performed. For the subset patients who will have DCE-MR, the imaging sequence and time for DCE-MRI (~10-15 minutes) is not expected to change significantly from standard care of surgical treatment.

Risk of confidentiality breach: Subjects enrolled in research are always exposed to additional risks of a breach in confidentiality, for example, of some elements of their personal health information that is made available to study investigators as part of their participation. The risk is 100%, but the occurrence rate of an actual breach is < 1% (to date, we are not aware of any subject participating in our studies who has experienced a detrimental breach of confidentiality or confidential information).

Information about study subjects will be kept confidential and managed according to the requirements of the Health Insurance Portability and Accountability Act of 1996 (HIPAA). Risk of breach of confidentiality of the medical records and status of participants will be minimized. Databases which are used to store subject-sensitive information are password-protected and encrypted during file/data transfers from viewing terminals. Access will be limited to research team members who have undergone CPHS training at Dartmouth. Whenever possible and practical standard-of-care clinical data used in the research will be de-identified when under analysis.

1.5.2 Potential Benefits

Patients enrolling in this study will not benefit directly because no diagnostic or therapeutic decisions will occur based on the study, and thus, administration of the study is not intended to alter the surgical procedure. However, future patients may benefit from the knowledge gained from the study since this study may provide an objective, intraoperative, and real-time methodology to assess bone perfusion and thoroughness of debridement. This method may save the patients from unnecessarily high risk for index infection or nonunion—in the setting of open fracture—or recurrent infection in the setting of established infection, due to the substantial practice variation.

2 Study Objectives

The primary study objective is to establish the range and variation associated with bone/soft tissue perfusion in fracture patients, using ICG fluorescence imaging and examine the relationship between perfusion and complications such as SSI, persistent SSI, and fracture nonunion.

The secondary study objective is to develop intraoperative hardware and software tools that will be used to guide debridement to optimize the quantity of bone/tissue resected to minimize complications.

3 Study Design

3.1 General Design

This study is a Phase I open label, single-center clinical trial of fluorescence imaging for predicting recurrent infection in musculoskeletal trauma patients. Patients who undergo fracture fixation or joint fusion or requiring open surgical debridement/saucerization for osteomyelitis, may be recruited into the study. Although the SPY Elite imaging system and the use of ICG have not been used in this type of study previously both have been established in other clinical settings to assess tissue perfusion. The expected duration for enrolling study participants is five years, and up to 300 subjects may be enrolled. Eligible consenting patients will receive standard of care treatment for their fracture or complication (infection or nonunion) including irrigation and debridement of their operative site. Detail study procedures will be described in the following Section 6.

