Methodology	
This will be a prospective observational trial to better understand the range and variation associated with bone/soft tissue perfusion in fracture patients and examine the relationship between perfusion, measured using quantitative Indocyanine green (ICG) fluorescence and complications such as surgical site infection (SSI), persistent SSI, and fracture nonunion. Primary outcome measure is complication (either infection, recurrent infection or nonunion).
 
Eligible consenting patients will receive standard of care treatment for their fracture or infection including irrigation and debridement of their operative site and/or fracture fixation. Participation in this study has no specific benefit to the subject. This treatment is not expected to alleviate the need for surgical intervention. After exposure, 0.1 mg/Kg ICG will be injected intravenously and video rate ICG fluorescence images will be acquired 20 seconds before and 4 minutes after the injection, each before and after debridement. A subset of 38 post-fracture complication patients will undergo surgical treatment for their infection in Center of Innovation Surgery (CIS) and have either an intraoperative DCE-MRI after exposure but before the ICG injection or a preoperative DCE-MRI. Patients receiving surgery in the CIS will be required to sign an additional CIS-specific consent document, Informed consent with MRI.
 
The need for repeat surgical procedure will be left up to the treating surgeon. If repeat procedure is needed, pre- and post-debridement quantitative ICG fluorescence images will be obtained at each procedure.
 
Study participants will be followed at 2 weeks, 6 weeks, 3 months and 6 months from their index study surgery. Complication including index infection, recurrent infection or delaying union/nonunion will be identified at the time of diagnosis and/or during each participant's assessment that occurs during routine outpatient clinic visit. Detailed information on the infection including date of diagnosis, participant signs and symptoms, culture test results, method of treatment(s), and date of resolution will be documented.

Study Duration	Five years
Study Center(s)	Single-center, Dartmouth-Hitchcock Medical Center

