Objectives	The primary study objectives are to (1) establish the range and variation associated with bone/soft tissue perfusion in fracture patients and (2) examine the relationship between perfusion, measured using quantitative ICG fluorescence and complications such as SSI, persistent SSI, and fracture nonunion.
Number of Subjects	(1) 176 patients with open fracture patients; (2) 82 patients with a complications (infection or nonunion) following surgical treatment of fracture; (3) 100 patients with closed fracture.

Diagnosis and Main Inclusion Criteria	
Open Fracture Cohort (Cohort 1)
 
 a. Patients 18 years of age or older. b. Open extremity fracture. c. Planned definitive fracture management with external fixation, internal fixation, or joint fusion. d. Will have all planned fracture care surgeries performed by a participating surgeon or delegate. e. Provision of informed consent. 
Complication Cohort (Cohort 2)
 
 f. Patients 18 years of age or older. g. Extremity fracture. h. Prior definitive fracture management with external fixation, internal fixation, or joint fusion. i. Superficial, deep, or organ space SSI (as per CDC criteria) at the fracture site that requires operative management. j. Will have all fracture care surgeries performed by a participating surgeon or delegate. k. Provision of informed consent. 
Closed Fracture Cohort (Cohort 3)
 
 l. Patients 18 years of age or older m. Closed extremity fracture n. Planned definitive fracture management with external fixation, internal fixation, or joint fusion. p. Provision of informed consent.
Study Product, Dose, Route, Regimen	
This protocol is an imaging study which does not specify any change in treatment protocol or and will not alter the surgical course for the patient enrolled, therefore should not be considered an experimental treatment..
 
ICG is an FDA approved fluorescence probe. After skin exposure, 0.1 mg/Kg ICG will be injected intravenously, each before and after debridement. Video rate ICG fluorescence images will be acquired 20 seconds before and 4 minutes after ICG injection, by an FDA approved fluorescence imaging system, (Spy Elite (Novadaq/Stryker US). The imaging is non-contact and the imaging head is at least 50 cm away from the bone.

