7.1 Sample Size Determination

The participating Statisticians on the study are members of the Norris Cotton Cancer Center and/or Department of Orthopaedics at Dartmouth-Hitchcock Medical Center. Sample size determination is based on the primary objective of the study as a pilot assessment of ICG fluorescence intensity of bone perfusion.

For patient cohort 1, we anticipate that approximately 10% of patients with open fracture will have an SSI within 12 months of their fracture^{1, 2, 32}. A total sample size of 160 patients will result in an estimated 16 patients with an SSI and 144 patients without an SSI. We will have 86% statistical power to detect a mean maximum fluorescence intensity (I_{max}) difference of 24 (a.u.) between the SSI group and the non-SSI group with an estimated standard deviation of 30 (a.u.) and 15 (a.u.), respectively. All parameters were obtained from our previous porcine study. To be conservative, we increased the standard deviation by 50% for this power calculation. The type I error is set to be 5%. If we assume a drop-out rate of 10%, then a total of 176 patients will be enrolled.

For patient cohort 2, we anticipate approximately 30% of patients with an SSI will go on to develop a persistent SSI/treatment failure within 12 months of diagnosis of their SSI¹². Based on this estimate, a sample size of 22 patients with SSIs and 52 patients without, will have 93% statistical power to detect a mean I_{max} difference of 24 (a. u.) between the persistent SSI/treatment failure group and the non-persistent SSI/non-treatment failure group with I_{max} estimated standard deviation of 30 (a. u.) and 15(a. u.). All parameters are obtained from our previous porcine study, which are consistent with a pilot study conducted at STC in human participants using ICG fluorescence for a different indication. To be conservative, we increased the standard deviation by 50% for this study. The type I error is set to be 5%. If we assume the dropout rate is 10%, then a total of 82 patients will be recruited.

For patient cohort 2-1, the strength of the relationship between DCE-MR and DCE-FI measurements will

be assessed by determining the zero-order correlation and resulting R2 metric. A sample of 21 was estimated utilizing formula presented by Bonett & Wright ³⁶ with a Type I error rate of 0.05 and Type II error

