rate of 0.20 (1-Power) to estimate the magnitude of zero-order correlation and interval estimation. Formula inputs included expected zero-order relationship of $r = 0.85$ (95% CI 0.55 to 1.00). To optimize the imaging parameters of DCE-MRI, extra seven patients has been added into this cohort. Thus, total of 30 patients will be involved in this cohort.

Patient cohort 3 will serve as the control group for cohorts 1 and 2.

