Table 7.2: Summary of Outcome Analysis Plan of patient cohort 2.

Objective	Outcome		Hypothesis	Method of analysis
	Name	Type		
Determine the association between post-debridement bone perfusion as measured by quantitative ICG fluorescence and persistent SSI/treatment failure in patients with SSI	Persistent SSI/Treatment failure	Binary	Mean perfusion will be lower among fracture patients with persistent SSI/treatment failure	Students t-test Logistic regression

Patient cohort 3: Classification into cohort categories (closed fracture, open fracture, complication) is the independent variable and ICG fluorescence magnitude is the dependent variable. Descriptive statistics, including means and standard deviations, will be presented with 95% confidence intervals.

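### The three cohort targets add to 358, but enrolment is planned and capped at 300; the MRI subset is given as both 38 and 30

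*Combined protocol and SAP*

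**What the plan says.** **Total.** Section 3.1 (General Design) sets a ceiling: "The expected duration for enrolling study participants is five years, and up to 300 subjects may be enrolled". Section 1.4 (Dose Rationale) gives the same number as the plan: "We plan a sample size of 300 patients in this open label, single center, clinical trial".

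**Cohorts.** The Number of Subjects row of the Study Summary lists 176 open-fracture patients, 82 patients with a complication, and "3) 100 patients with closed fracture". Section 7.1 arrives at the first two independently. For cohort 1: "If we assume a drop-out rate of 10%, then a total of 176 patients will be enrolled". For cohort 2: "If we assume the dropout rate is 10%, then a total of 82 patients will be recruited". For cohort 3 it gives a role but no size: "Patient cohort 3 will serve as the control group for cohorts 1 and 2". Section 7.2 then sets up a comparison across all three cohorts: "Classification into cohort categories (closed fracture, open fracture, complication) is the independent variable and ICG fluorescence magnitude is the dependent variable".

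**MRI subset.** The Methodology row of the Study Summary refers to "A subset of 38 post-fracture complication patients". Section 6 puts the subset at 30. Section 7.1 starts from 21, adds seven patients for tuning the imaging parameters, and also states 30.

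**The concern.** A ceiling of 300 and cohort targets adding to 358 are both current text, and no passage reconciles them. The approving committee and the monitors therefore have no single accrual total. If the team recruits to the cohort targets, it passes the stated ceiling at patient 301. If it stops at 300, at least one cohort closes short, and the protocol does not say which. The choice has statistical consequences: either the control group shrinks by more than half, or a cohort with a stated power does not reach the number that power was based on. A choice made during accrual, with some outcomes already visible, is worse than one fixed in advance.

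The MRI discrepancy is separate. The subset lies inside cohort 2, so it changes neither the total nor the power. It does leave the number of patients assigned to contrast MRI unclear by 8.

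**Working it through.** **1. The plan's own cohort figures (Section 7.1).**
- Cohort 1: 160 evaluable × 1.1 = 176.
- Cohort 2: 22 + 52 = 74 evaluable; 74 × 1.1 = 81.4, rounded up to 82.
- Power inputs: difference 24 a.u., SD 30 in the event group and 15 in the other, type I error 5%. Section 7.1 does not state sidedness. I used the Welch test, with power from the noncentral t distribution: SE = √(30²/n₁ + 15²/n₂), noncentrality = 24/SE.

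| Cohort | n₁ / n₂ | SE | Noncentrality | Two-sided power | Stated |
|---|---|---|---|---|---|
| 1 | 16 / 144 | 7.60 | 3.16 | 84.1% | 86% |
| 2 | 22 / 52 | 6.73 | 3.57 | 92.9% | 93% |

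Both targets reproduce, and both powers agree within two points.

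**2. The total.**
- 176 + 82 + 100 = 358.
- 358 − 300 = 58, which is 58/358 = 16% of the listed patients.
- Cohorts 1 and 2 use 176 + 82 = 258 places, leaving 300 − 258 = 42 for cohort 3.

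**3. Could the gap be explained?**
- *Drop-out.* Without any allowance, 160 + 74 + 100 = 334, still above 300.
- *MRI subset.* It is part of cohort 2 and adds nothing to 358.
- *Patients counted in two cohorts.* The documents do not provide for this. It would take 58 such patients. Cohort 1 expects 10% infections, at most about 18 of 176. If all of them re-entered cohort 2, about 358 − 18 = 340 different patients would remain.

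**4. If cohort 3 takes the whole cut (100 to 42, a 58% reduction).** The stated powers of cohorts 1 and 2 are unaffected. The 95% CI half-width for the control mean is t × SD/√n. The documents give no SD for cohort 3, so I take 15 and 30 as a range.

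| n | t | SD 15 | SD 30 |
|---|---|---|---|
| 100 | 1.984 | 2.98 | 5.95 |
| 42 | 2.020 | 4.67 | 9.35 |

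The ratio is 4.67/2.98 = 1.57, whichever SD is used.

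**5. If the cut is shared in proportion (an illustration; the documents give no split).** Multiplying by 300/358 = 0.838 gives 147 / 69 / 84. I apply 10% loss and event rates of 10% and 30%, and leave group sizes fractional.

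| Cohort | Enrolled | n₁ / n₂ | Two-sided power | One-sided power |
|---|---|---|---|---|
| 1, full | 176 | 15.8 / 142.6 | 83.7% | 91.2% |
| 1, reduced | 147 | 13.2 / 119.1 | 75.6% | 85.8% |
| 2, full | 82 | 22.1 / 51.7 | 93.1% | 96.7% |
| 2, reduced | 69 | 18.6 / 43.5 | 87.9% | 93.7% |

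**6. MRI subset.** 21 + 7 = 28, not 30. An unstated 10% allowance on the 21 (21 × 1.1 = 23.1, taken as 23; 23 + 7 = 30) could explain 30, but that is a guess. Nothing shown leads to 38, and 38 − 30 = 8.

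**The case against.** The strongest reply is that the powered part of the trial does not conflict with 300. The Study Summary and Section 7.1 agree on 176 and 82, and 258 fits under the ceiling. Only the 100 for cohort 3 causes the clash. That number appears once, has no derivation, and supports an analysis for which Section 7.2 names only descriptive statistics. On this view cohort 3 would absorb the cut and both stated powers would survive. This is correct as far as it goes: the targets for cohorts 1 and 2 are consistent, and the missing accrual target is the total. But the protocol nowhere says that cohort 3 gives way, and the control group would then have 42 patients instead of 100.

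The power losses under a proportional cut are hypothetical, and they depend on sidedness. The hypotheses in Section 7.2 are directional. One-sided power after the cut (85.8% and 93.7%) is essentially the stated 86% and 93%. However, the stated powers at full enrolment match the two-sided calculation better, so under the cut the design would probably lose power relative to what was planned. These figures illustrate what is at stake; the contradiction does not depend on them.

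The half-widths for cohort 3 allow for no drop-out. With 10% loss they run from about 3.1 to 4.9 (SD 15) and from 6.3 to 9.9 (SD 30), and the ratio is essentially unchanged.

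On MRI, Section 6 lets a scan from the 48 hours before surgery replace the intraoperative one, and Section 1.4 says only that subset patients may have contrast MRI. Subset size therefore does not fix the number of additional scans. Still, the Study Summary assigns the whole subset to one kind of contrast MRI or the other, so the planned number remains unclear by 8.

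**Conclusion.** The concern holds. The sum of 358 against a plan and ceiling of 300 is plain arithmetic on current text, and neither drop-out, the nested MRI subset nor double counting closes the gap of 58. Cohorts 1 and 2 can keep their targets under 300 only if cohort 3 has 42 patients or fewer. The 57% widening of the control interval does not depend on the assumed SD; the half-widths in a.u. do. The fall to about 76% and 88% two-sided power rests on an assumed proportional split and on the effect size and SDs in Section 7.1. The MRI subset size is inconsistent as well (38, 30, and components that give 28), without effect on the total or the power. This should be corrected, but it does not undermine the design of cohorts 1 and 2.

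**What to change.** 1. State one total in the Study Summary, Section 1.4 and Section 3.1, with cohort sizes that add to it. There are two routes:
   - *Use 358.* This adds no patients beyond those the Study Summary lists, but it is 58 more than Sections 1.4 and 3.1 state, so the approved ceiling may need amending.
   - *Keep 300.* Give revised cohort sizes and the power that cohorts 1 and 2 then have. If cohort 3 takes the whole cut, the sizes are 176 / 82 / 42 and both stated powers stand. The 42 is only what is left over, so the team should confirm that it is enough for a control group.
2. State the size of cohort 3 and its basis in Section 7.1, for example the precision wanted for the control mean.
3. Give one MRI subset size in the Study Summary, Section 6 and Section 7.1, with every step from 21 to the final number shown.

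The cost is a text correction, plus either a possible amendment of the ceiling (358) or a smaller control group or lower stated power (300).
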